2.2. Secondary aim

To evaluate the sensitivity of candidate tasks to refine treatment targets and identify predictors of treatment response from ION-ASD. The long-term goal of this aim is to support development of a brain-based behavioral toolbox for use in future intervention research on social learning in youth with ASD. The goals in this proposal will investigate 1) putative treatment targets associated with change following ION-ASD and 2) pre-treatment factors predictive of response to ION-ASD. We predict treatment response in ION-ASD, as defined by a clinical global impression improvement score of <2 (improved to very much improved, and 25% improvement on the Social Skills Improvement System (SSIS), will be associated with improvement on candidate tasks of social-emotional perception, attention to eye region, mental state attributions, and affiliation.

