*Clinical Global Impressions – Improvement Scale - Global (CGI-I)*⁵⁴. The CGI-I employs a seven point (1 = very much improved to 7 = very much worse) to determine the patient's improvement in response to treatment. The CGI-I has been successfully used as an outcome measure in previous psychopharmacology trials including the RUPP trial of risperidone in children with ASD, and the STAART funded citalopram trial. The rating convention for assigning CGI scores is to use all available data including direct observation, scales, and patient report to inform clinical judgment. CGI-I, Global will be used to evaluate safety, with the requirement that individuals scoring CGI of 6 or greater for 2 or more weeks be discontinued from the study and provided with appropriate referrals. CGI ratings will be made by unblinded clinicians conducting safety evaluations and blinded raters.

Blinded CGI-I ratings will incorporate semi-structured questions to evaluate social conversational and social behavioral skills. Questions will be based on the Bates & Reilly conversational task (Reilly, Bates, & Marchman, 1998). Blinded CGI ratings will be recorded to code narrative discourse and quality in collaboration with the social communication lab of [name]. Social Functioning

2. Social functioning

- a. *Social Skills Improvement System (SSIS)*. The SSIS is an informant-report that evaluates social skills, problem behaviors, and academic competence in youth ages 3-18 years old. The SSIS is a multi-rater with reports provided by caregivers, teachers, and students. The form takes 10-25 minutes to complete. The scale is designed to identify social impairments for intervention development and tracking.

3. Quality of Life

- a. *Caregiver Strain*⁵⁹. The CSQ assess family stress and was developed for caregivers of children with developmental disabilities.

Exploratory Outcome Measures

1. Social Function

- a. *Autism Impact Measure*⁶⁰. The AIM is a 25-item caregiver report assessment of the frequency and impact of core ASD symptoms in children with ASD. This new measure is designed to assess recall of core symptoms within two-week intervals and will be used as an exploratory measure of changes in core ASD symptom presentation in this study.

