8.9. Sample size considerations

Based on data from the NETT trial, published trials in sustained OT treatment⁵⁴, and single-dose challenge studies in autism⁴⁹ we expect our sample size (n=25/group with 5% attrition) to yield 80% power to detect a difference in means of 0.40, assuming a standard deviation of differences of 0.670, with a 0.050 two-sided significance level. Although potentially underpowered, we believe data from this trial will provide important information on safety, tolerability, and treatment targets from a novel, multi-dosing OT-combined treatment strategy. Specific Aim 2 (treatment targets, pre-treatment factors predictors). Repeated measures ANOVAs will be conducted to evaluate group differences on social behavior and social cognition composites, social recognition, mental state inference, affiliation, social reward and social competence (i.e. SSIS) in order to identify potential treatment targets for the combined treatment approach. Factors predicting treatment response will include global scores on all baseline measures. Responder status will be entered as a categorical variable as defined above (CGI-I≤2 + SSIS > 25%). PCA will be conducted on significant baseline predictors to develop composite variables and used to predict response using logistic regression.

Confidential

Rush University Medical Center

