Data Analysis. Primary: Composite scores of both primary outcomes (i.e., SBI and SC) will be used as the response (i.e., outcome) variable in a series of mixed-effects linear regression models using the *lmer* package in *R Studio* to assess the effect of treatment condition (ION-ASD vs. Facilitated Play), time (e.g., change from baseline after 12 weeks), and condition X time interaction. Across all models, the individual participant will be included as the random effect. Age, verbal IQ, ADHD and generalized anxiety (from the Child & Adolescent Symptom Inventory-5 [CASI-5] T-scores) will be entered into the model to be examined as potential covariates and/or moderators to outcomes as in prior work. We will estimate effect sizes (standardized Betas) and confidence intervals (95%) acknowledging the likelihood that analyses may not permit definitive conclusions given the likely size of the confidence intervals. Finally, if the statistical assumptions of the model are not met (e.g., homoscedasticity, normality, linear relationships), generalized linear models with appropriate link functions or potential transformations of predictor variables will be assessed.

Secondary Outcomes. The linear mixed-effects models will also be used on secondary outcome measures: SRS T-score, mean Caregiver Strain Global rating scale. Responder (i.e., Clinical Global Inventory-Improvement [CGI-I]) analysis will be conducted using either a Chi-squared or Fisher's exact test (when observations are small such that $>20\%$ of cells have *expected* count <5) on the number of responders (i.e., CGI-I scores of 1-2) versus non-responders (i.e., CGI-I scores of 5-7) by group.

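### Aim 2 tests baseline SSIS as a predictor of a response defined partly by SSIS improvement, so its association with response is inflated by construction

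*Protocol*

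**What the plan says.** Protocol 2.2 sets as one goal of the secondary aim to find "pre-treatment factors predictive of response to ION-ASD", and describes response as a CGI-I criterion together with "25% improvement on the Social Skills Improvement System (SSIS".

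Protocol 8.9 gives the analysis:

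- Predictors: "Factors predicting treatment response will include global scores on all baseline measures".
- Outcome: "Responder status will be entered as a categorical variable as defined above (CGI-I≤2 + SSIS > 25" per cent).
- Model: "PCA will be conducted on significant baseline predictors to develop composite variables and used to predict response using logistic regression".

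Appendix A schedules the SSIS at baseline and at weeks 12, 16 and 24, so it is one of the baseline measures. Neither document removes it from the predictor set. Section 4.2 says that the SSIS "evaluates social skills, problem behaviors, and academic competence in youth", but no section says which of these scores carries the 25% rule.

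The SAP has no analysis of predictors of response. Its only responder analysis compares "responders (i.e., CGI-I scores of 1-2) versus non-responders (i.e., CGI-I scores of 5-7) by group", with no SSIS term.

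**The concern.** The protocol does not spell out what 25% improvement is measured against. The natural reading is percent change from the child's own baseline. On that reading the baseline SSIS score is both the denominator of the outcome and a candidate predictor of it. For a higher-is-better score, two effects then push in the same direction:

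- a child who starts low needs fewer points to gain 25%;
- a low observed score tends to rise on retest, because part of it is measurement error.

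This is not a multiplicity problem. It would remain if SSIS were the only predictor tested, and a multiplicity correction would not remove the bias.

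Aim 2 is meant to inform later intervention research. A report that children with weaker social skills respond better to ION-ASD is plausible enough to be believed and could steer enrichment of a later trial. Because 8.9 passes significant predictors on to a composite and a logistic model fitted to the same response, the bias would not stay in a single univariate test.

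**Working it through.** **The plan's own figure.** Section 8.9 gives no figure for the predictor analysis. Its one power statement (25 per group, 5% attrition, difference 0.40, SD of differences 0.670, two-sided 0.05, 80% power) reproduces as a one-sample or paired t-test: 80.0% at n = 24. It does not bear on Aim 2 and is used here only for sample size.

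**Sample size in the ION-ASD arm.**
- From 8.9: 25 × 0.95 = 23.75, about 24.
- From 2.1 (80 randomised) with 1:1 allocation: 40, and 40 × 0.95 = 38.

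**Denominator effect.** Points needed = 0.25 × baseline. Take SD/mean = 0.20 as an illustration and scale the mean to 100, so that SD = 20. A child one SD below the mean (80) needs 0.25 × 80 = 20 points, or 1.0 SD. A child one SD above (120) needs 0.25 × 120 = 30 points, or 1.5 SD.

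**Regression to the mean.** Let baseline and follow-up have equal variance s² and retest correlation r, with the same true gain for every child. Then:
- cov(baseline, change) = −(1 − r)s²
- var(change) = 2(1 − r)s²
- corr(baseline, change) = −√((1 − r)/2)

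At r = 0.70 this is −√0.15 = −0.387. At r = 0.85 it is −√0.075 = −0.274. These correlations arise with no true relation between baseline and gain.

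**False-positive rate under the combined rule.** Assumptions, none of which the documents give: higher-is-better score, SD/mean 0.15-0.25, r 0.70-0.85, equal true gains of 0.5-1 SD, and CGI-I of 2 or less in 70% of children independently of SSIS. Response is a gain above 25% and a favourable CGI-I. Baseline SSIS is tested against response at two-sided 0.05, and all simulated trials are counted.

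| Response | n = 24 | n = 38 |
|---|---|---|
| CGI-I and SSIS gain above 25% | about 6-41% | about 14-64% |
| CGI-I alone | about 5% | about 5% |

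The lowest rates occur where spread and gain are small and very few children respond.

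**Sensitivity of the combined rule.** A second set of runs used SD/mean 0.15-0.25, reliability 0.6-1.0, mean gain 10-20% of the scale mean, and CGI-I of 2 or less in 50%.

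| Scenario | n = 24 | n = 40 |
|---|---|---|
| Equal point gains for all | 3-30% | 8-49% |
| Point gains varying between children | 13-22% | 24-37% |
| Gains proportional to baseline | 3-16% | 4-25% |
| Lower-is-better score | 3-12% | 4-22% |

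With varying point gains, the spurious slope was negative in 88-96% of evaluable trials. With proportional gains and error-free measurement there was no inflation. With CGI-I alone as the response, rates were 4.4-5.6% throughout.

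**Would adjusting the other predictors for baseline SSIS help?** Consider a measure correlated 0.6 with SSIS through the child's true level, at n = 38. Unadjusted, it is falsely significant in 3-13% of trials. Adding baseline SSIS as a covariate raises the rate at r = 0.70, for example from 9% to 15-16%.

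**The case against.** The strongest points on the other side are these.

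- **Equal point gains are a choice of null.** If every child gains the same number of points, a low-baseline child really is likelier to meet a percent criterion. That part reflects the metric, and only retest regression is pure artefact. This stands. It is why the proportional-gain results are shown, and they still reach 25% at n = 40 when measurement is imperfect.
- **The SSIS score is unspecified.** For a problem-behaviour score the two effects partly cancel. This stands too, although 8.9 lists the SSIS as a measure of social competence, which favours the social-skills reading.
- **CGI-I is also required.** This dilutes the artefact but does not remove it. The combined-rule figures already include it.
- **The SAP uses CGI-I alone.** That definition has no such coupling, but it serves a group comparison and does not replace the Aim 2 predictor analysis.
- **The stakes are limited.** This is a secondary aim of a pilot that calls itself potentially underpowered, and no primary or safety result depends on it. That limits the priority of the point but does not answer it.

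A reader might infer that baseline SSIS is bound to appear predictive, or that every correlated baseline measure is contaminated and should be adjusted for baseline SSIS. The documents support neither. The inputs that fix the rate are not given, and in most plausible settings the false-positive rate is well short of certainty. Leakage to other measures depends on how they correlate with SSIS. Where they share its measurement error it can be material (7-26% at n = 38), and adjustment then helps (2-6%). Where they track the true level it is small, and adjustment can create the opposite bias.

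**Conclusion.** The point holds in a limited form. As written, and on the percent-change reading, the test of baseline SSIS as a predictor of Aim 2 response is biased by construction. For a higher-is-better score with equal true point gains, its false-positive rate is roughly 6-41% at n = 24 and 14-64% at n = 38, against 5%. The inflation is smaller with proportional gains or a lower-is-better score, and absent with proportional gains and no measurement error.

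All these figures rest on assumed SSIS spread, reliability and gain, and on CGI-I being independent of SSIS. Section 4.2 lets CGI raters use all available data, including scales, so that independence is itself an assumption. The primary comparison is unaffected. The change should be made because the error is avoidable at almost no cost.

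**What to change.** In Protocol 8.9:

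1. Exclude baseline SSIS, total and subscales, from the predictors of the SSIS-based response.
2. Run the same predictor models with blinded CGI-I of 2 or less alone as the response, and examine baseline SSIS as a predictor only there.
3. Name the SSIS score to which the 25% rule applies, and state that the change is measured from baseline if that is meant.
4. Reconcile the responder definition with the SAP. The SAP uses CGI-I alone and places scores of 3 and 4 in neither class, so the text should say how those children are counted.

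Do not add baseline SSIS as a fixed adjustment term in every other predictor model. With an error-prone baseline this can introduce the opposite bias.

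The cost is a few sentences and no new data, since the SSIS and blinded CGI-I are already scheduled. The downside is that one candidate predictor is lost for the composite response.

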2.3. Exploratory aim

To assess maintenance of treatment effects from ION-ASD. Effects on social-communication behaviors and social cognition will be evaluated at 1- and 3- month post-treatment to evaluate the relationship between changes in domains underlying social learning and durability of treatment effects. This exploratory aim probes evidence indicating persistent effects of oxytocin in pilot studies of multi-dose OXT treatment in adolescents with ASD⁴⁰ and translational data indicating long-term developmental effects from peripheral oxytocin administration during early development³⁵.

At the conclusion of this study, we expect to develop a safe, feasible, and socially valid multi-modal treatment protocol for core social impairments in youth with ASD. The treatment protocol seeks to enhance the automaticity of social learning processes required to negotiate interpersonal interactions. Data will inform selection of outcomes tapping into hypothesized mechanisms and predictors of treatment effects, as well as advance combined psychosocial and pharmacologic treatment approaches to ASD.

3. Study Overview

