3.1. Study Design

This is a two-phase, 3 year, randomized, single-blind, parallel group, contact controlled pilot trial of OXT augmentation of CBI groups in youth with ASD. Phase 1 (n=10) is an initial development trial to refine manuals, procedures, and outcome evaluations. Phase 2 (n=70) will evaluate feasibility, safety, and preliminary efficacy of ION-ASD relative to the contact control (i.e. social play group). All participants are expected to be outpatients and will participate in a 12-session group therapy, with a follow-up study visit at 24 weeks. Evaluations will be conducted at four time points: Screening, Baseline, Endpoint (week 12), and Follow-up (1-month & 3-months post-treatment).

Each phase will randomly assign in a 1:1 ratio to either ION-ASD or control in blocks of 10. Efficacy outcomes will be evaluated by both caregiver report and blinded independent evaluators (IE); safety assessments will be conducted by unblinded treating medical clinicians (Medical TC). Caregivers and participants will be instructed to conceal group assignment from IEs. IEs, participants, and caregivers will also be instructed on reporting strategies should group assignment be revealed. Corrective action plans in these scenarios will be employed if necessary and include changing IE raters and flagging data. IEs will be asked to “guess” patient conditions at the end of the trial to evaluate integrity of the blind.

Medical TCs will monitor side-effects using weekly ratings with the participant and caregiver. Clinical IEs will evaluate global functioning and social communication skills. Neurocognitive IEs will conduct blinded neurocognitive assessments (see Appendix A: Time & Events Schedule).

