3.5. Randomization

This pilot study will recruit 90, youth with ASD ages 8-11 years old into a randomized, parallel group design of 1) ION-ASD and 2) control group – facilitated play. A feasibility trial will be conducted with the first 10 participants to refine the protocol including finalizing measures to support Aim 2 (brain-based behavior

Confidential

Rush University Medical Center

toolbox). If substantial protocol revisions are made, modifications to the protocol, consent, and IND will be made before proceeding with recruitment.

Participants will be randomized 1:1 to ION-ASD or control. After eligibility is confirmed and consent is obtained, eligible participants will be assigned a study randomization number according to computer-generated randomization list.

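### The Aim 2 predictor search screens all baseline measures without multiplicity control or validation, so with no true predictor about 25-55% of trials would still report a significant composite

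*Protocol*

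**What the plan says.** Protocol Section 2.2 makes it a secondary goal to find "pre-treatment factors predictive of response to ION-ASD". The method is in Section 8.9: "Factors predicting treatment response will include global scores on all baseline measures", followed by "PCA will be conducted on significant baseline predictors to develop composite variables and used to predict response using logistic regression". Responder status there is a CGI-I of 2 or less plus more than 25% improvement on the SSIS.

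Section 8.9 gives no screening test or level, no adjustment for the number of measures, and no hold-out, resampling or permutation step. The measure list is provisional: Section 3.5 describes the first 10 participants as serving, among other things, for "finalizing measures to support Aim 2".

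The SAP does not contain this analysis. Its only use of pre-treatment variables is four named covariates or moderators (age, verbal IQ, ADHD, generalized anxiety) in the models for the primary composites. Its only responder analysis compares the two groups on CGI-I.

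**The concern.** Selecting variables because they are significant, and then testing a composite of the survivors in the same data, gives a p-value that takes no account of how many variables were tried. With a score of candidates and a few dozen children, chance alone will often supply a survivor. The survivor, or the first component of several, will then usually look significant again, with good apparent discrimination.

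The stake is the credibility of whatever Aim 2 reports as a predictor of response. Section 2.2 says the aim is to support future intervention research, and Section 2.3 expects that "Data will inform selection of outcomes tapping into hypothesized mechanisms and predictors of treatment effects". A chance finding could therefore shape later work. The primary comparison and the safety analyses do not depend on this step.

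**Working it through.** **The plan's own figure.** Section 8.9 gives one design figure: "n=25/group with 5% attrition", for 80% power at a difference of 0.40 with an SD of differences of 0.670. As a one-sample (paired) t-test this reproduces: 0.40/0.670 = 0.597 SD, and with 25 × 0.95 = 23.75, about 24 children, power is 79.98%. No error rate or power is stated for Aim 2, so the figure serves here only as the source of n=24.

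**Inputs.**
- Sample size: 24 (above); 35, half of Phase 2 ("Phase 2 (n=70) will evaluate feasibility, safety, and preliminary efficacy of ION-ASD relative to the contact control"); or 70, if both arms are pooled.
- Candidates: Appendix A marks 12 parent questionnaires and 6 participant tasks at screening or baseline, 12 + 6 = 18. Adding ADOS-2/CARS2, ADI-R, IQ and CGI-S would give 22, but Section 4.1 reserves CGI-S for eligibility. Against that, the Baseline Visit text in Section 5.2 adds BASC-3, GEMEP and sensor-based tests. The range 18-22 is therefore a working assumption.
- Not in the documents, so assumed: screen at p < 0.05, correlation 0-0.5 between measures, 25-50% responders, one retained component, Wald final test at 0.05.

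**Step 1: the screen alone.** With independent measures, P(at least one false survivor) = 1 − 0.95^m.
- m = 18: 1 − 0.95^18 = 60.3%, with 18 × 0.05 = 0.9 false survivors expected.
- m = 22: 1 − 0.95^22 = 67.6%, with 22 × 0.05 = 1.1 expected.

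Correlation between measures lowers these rates.

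**Step 2: the whole sequence, no true predictor.** Simulated as: screen each measure, take the first principal component of the survivors, test it by logistic regression on the same outcome.
- Across 18-22 measures, n = 24-35: about 25-55%. Single cells at the edges reached about 23% and 57% in runs of limited size.
- Pooled arms, n = 70: up to about 58%.
- A single prespecified null predictor under the same test: 2.4-4.5%.

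For 18 measures, correlation 0.3 and 40% responders:

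| n | Significant composite | In-sample AUC in those trials | Nested cross-validated AUC in the same trials |
|---|---|---|---|
| 24 | 35-36% | 0.81-0.82 | 0.55-0.59 |
| 35 | 42% | 0.76 | 0.55-0.57 |
| 70 | 47% | 0.68 | 0.54 |

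Over all null trials the cross-validated AUC is 0.50, as it should be.

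**Step 3: where the inflation arises.** At n = 24, 18 measures, correlation 0.3 and 40% responders, 49% of null trials have at least one survivor and 35% end with a significant composite. The final test removes some false survivors and adds none. It is still not confirmation, because it reuses the outcome that chose its inputs.

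**Sensitivity.** At correlation 0.7 and n = 25 the rate falls to about 16-17%, still over three times 5%. A likelihood-ratio final test raises the top of the range to about 67%.

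**Step 4: the remedy.** Permuting responder status and rerunning the whole sequence (18 measures, correlation 0.3, 25% or 40% responders) brings the false-positive rate to 5.1% pooled (3.8-7.7% by cell), against 26-48% unpermuted.

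**The case against.** The best case for leaving the plan alone is that this is a proof-of-concept pilot. It speaks of candidate tasks, expects further studies, and nowhere calls the logistic step confirmatory. It also concedes low power and wide confidence intervals, and the SAP may have dropped the analysis. This limits the consequence but does not remove the error. The interval caveat in Section 8.8 belongs to the mixed models for Aim 1 and the exploratory aim. The low-power caveat in Section 8.9 concerns missed effects, not false ones. The SAP's silence neither withdraws nor repairs the Section 8.9 text.

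Some stronger readings are tempting and are not supported:
- A reader might infer that testing twice on the same responders itself drives the error rate. Step 3 shows that it does not exceed the screen's own rate.
- A reader might blame that reuse for the large odds ratios in false-positive trials (median 4.2-5.1 per SD at n=24). A single prespecified null predictor, kept only when significant, gives nearly the same (3.7-4.5).
- A reader might take 22 as the protocol's count. The documents state no count, and CGI-S should not be in it.
- A reader might take Section 2.3 to promise selection of predictors. What it says will be selected is outcomes.
- A reader might see three conflicting responder definitions. Sections 2.2 and 8.9 both include the SSIS criterion. They differ in the CGI-I cut-off: Section 2.2 has "as defined by a clinical global impression improvement score of <2", yet its own gloss spans more than one improvement category, which fits 2 or less. The SAP definition belongs to a separate by-group analysis.

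**Conclusion.** The concern holds for the secondary predictor aim only. Followed as written, Section 8.9 would report a significant predictor composite in about 25-55% of trials with no true predictor, if run in an ION-ASD arm of 24-35, and in up to about 58% with pooled arms. That is roughly 5 to 11 times the nominal 5% (25/5 and 55/5). The apparent AUC would overstate discrimination as well.

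That the screen is unadjusted and unvalidated follows directly from the two documents. The percentages rest on the assumed screening level, number of measures, correlation, response rate and final test, and would move with them. No combination examined brought the rate near 5%. A reader might extend this to the efficacy or safety conclusions; nothing in the documents feeds the predictor search into either.

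**What to change.** 1. State whether the Section 8.9 predictor analysis is still planned, since the SAP omits it.
2. If it is, fix in advance the list of measures, the arm or arms, the screening test and its level.
3. Run the whole screen-PCA-logistic sequence inside a permutation test of responder status (within arm if arms are pooled) and inside repeated cross-validation, repeating the screen each time.
4. Report the permutation p-value and the cross-validated AUC in place of the naive p-value and odds ratio, and label the result hypothesis-generating.
5. As a minor point, write one responder definition for Aim 2, reconciling the CGI-I cut-off in Sections 2.2 and 8.9.

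A Bonferroni level at the screen would also control the error (about 1.5-6% in the same kind of simulation), but it would leave the AUC uncorrected.

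The cost is a few sentences of text and some code, with no new data or visits. Fewer predictors will be declared, and power is modest. At 40% responders, the permuted sequence finds a lone predictor with an odds ratio of 3 per SD in about 31-39% of trials at n=35 and 70-84% at n=70. Power at n=24 was not simulated and would be lower than at n=35.
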